C. Secondary Objective:

i. To investigate the impact of SVG harvesting techniques – OVH vs. EVH on MACE, a composite endpoint of all-cause mortality, nonfatal myocardial infarction and repeat revascularization, at one and three-year postoperatively .

ii. To investigate the impact of SVG harvesting techniques – OVH vs. EVH on MACE, a composite endpoint of all-cause mortality, nonfatal myocardial infarction and repeat revascularization, over the entire follow-up period (active and passive) of the study postoperatively.

D. Secondary Hypothesis:

i. One-year composite MACE rate will be 6 percentage points lower in the open harvesting group and three-year composite MACE rates will be at least 8-10 percentage points lower in the open vein harvesting group compared to the endoscopic vein harvesting group.

ii. A significant smaller proportion of CABG subjects with SVGs harvested by open technique will experience MACE post-surgery compared to CABG subjects with SVGs harvested by endoscopic technique during the entire follow-up period

Other objectives are:

1. Investigate the impact of the two harvesting techniques - open vs. endoscopic - on clinical indicators of leg wound complications and subject satisfaction at six-weeks post-surgery; The hypothesis is the leg wound complications will be lower and satisfaction will be higher in the EVH group compared to OVH group.
2. Compare subject quality of life scores according to the SVG harvest technique at six-week post-surgery; the hypothesis is the subjects' quality of life scores will be higher in the EVH group compared to the OVH group.
3. Determine the role of vein harvester experience on clinical outcomes

IV. Importance of the Study Topic to the VA and Its Patients

CABG is the most common major surgical procedure in the U.S. and the VAMC Health System, and EVH is now the preferred modality of SVG harvesting in both the private sector and the VAMC (72%

EVH adoption rate in the VHA based on a 2009 survey commissioned by [name] at VACO). Decisions regarding the choice of coronary revascularization (CABG vs. percutaneous coronary intervention [PCI]) rest primarily on the anticipated failure rate of CABG versus PCI. The recent ARTS II trial (Serruys 2010) showed comparable freedom from MACE in selected patients undergoing multi-vessel PCI versus CABG.

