In the ROOBY study (CSP # 517) (Shroyer 2009), one year MACE rates were 9.9% in the OVH group and 15.3% in the EVH group ($p=0.0025$). The executive committee for the REGROUP study assumes that during the REGROUP study, 15.5% of the subjects in the EVH group will experience MACE in the first year post surgery. The committee also expects a 6 percentage point improvement in the one-year MACE rate in the OVH group.

B. Sample size calculation for the REGROUP study

To detect the expected 6 percentage point difference in one-year MACE rates between EVH (15.5%) and OVH (9.5%), a sample size of **545 in each group** will be required at 85% power, 5% type-I error rate and with a two-sided test. A sensitivity analysis was also done with various scenarios which are shown in the Table 3. Since, it would be possible to capture the majority of the MACE from the VA databases even if the subjects drop out before the one-year clinic visit, a relatively small inflation factor of 5% is used to inflate the sample size to account for the drop-outs. Approximately, 1150 subjects need to be randomized in the study to achieve the said power.

	Case 1	Case 2	Case 3	Case 4	Case 5	Case 6	Case 7	Case 8	Case 9
Tails	2	2	2	2	2	2	2	2	2
Proportion 1 (%)	9.9	9.9	9.9	9.5	9.5	9.5	10	10	10
Proportion 2 (%)	15.3	15.3	15.3	15.5	15.5	15.5	16	16	16
Alpha	0.05	0.05	0.05	0.05	0.05	0.05	0.05	0.05	0.05
Power (%)	90	85	80	90	85	80	90	85	80
Allocation ratio	1:1	1:1	1:1	1:1	1:1	1:1	1:1	1:1	1:1
Sample Size	792	677	592	637	545	476	659	563	492
Total Sample Size	1584	1354	1184	1274	1090	952	1318	1126	984
Attrition = 5%	1667	1425	1246	1341	1147	1002	1387	1185	1036
Attrition = 10%	1760	1504	1316	1416	1211	1058	1464	1251	1093
Attrition = 15%	1864	1593	1393	1499	1282	1120	1551	1325	1158

Table 3: Various sample size scenarios for the REGROUP study

Based on the one-year MACE rate difference between EVH and OVH groups as obtained from CSP 517, if we assume at the end of the active follow-up period (approximately 4.5 years from the beginning of the recruitment process) difference in survival rates (i.e., the proportion of subjects who will not experience

MACE) between the two harvesting groups will be approximately 8 percentage point (i.e., 83.5% in the EVH and 91.5% in OVH), a sample size of 532 per group will be required to achieve a power of 97.5%. So, the sample size of 1150 (with approximately 7% attrition rate accounted for) will provide adequate power to the time-to-MACE event primary outcome.

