Subjects who suffer any one of these three outcomes within the first year or in the first three years after the index CABG will be counted towards calculating the proportions of subjects with MACE (yes/no) in each harvesting technique group – subjects with endoscopic vein grafting or subjects with open vein grafting. Only the first event will be considered as the MACE event. These two proportions will be compared using a chi-square test.

Post-operative Leg Wound Complications: All subjects in both harvesting technique groups – EVH or OVH – will be examined for complications of the leg wound from harvesting at discharge and at six weeks post-surgery. Post-operative leg wound complication status (yes/no) will be recorded at discharge and at six weeks post-surgery. Proportion of subjects with leg wound complications will be computed for each treatment group and these proportions at each time point will be compared using chi-square tests. The impact of confounding variables, such as, BMI, diabetes status, smoking status, on the post-operative leg wound infection will be analyzed using a logistic regression.

Severity of Incisional Leg Pain: Severe leg pain, due to incisions made during vein grafting, data will be collected at discharge and at six-week post CABG. Proportion of subjects with severe pain (pain score 3 and above = yes) at each time point will be compared using chi-square statistics.

Quality of Life: QoL scores using VR-12 and Seattle Angina Questionnaire will be computed at baseline, six week, and 12 months post-surgery for the subjects in the two harvesting technique groups (EVH and OVH). Subjects in both groups will be categorized as "improved", "no change" and "worse" based on their baseline scores. The proportion of subjects in these three categories will be compared between the two groups using chi-square statistics. The actual scores from these measures will also be used to compare subjects in the two harvesting technique groups using analyses of covariance techniques, where the baseline (pre-surgery) scores will be used as a covariate.

E. Interim Monitoring

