2 STUDY OBJECTIVES AND ENDPOINTS

2.1 Study Objectives and Hypotheses

Primary Objectives:

Objective 1: To investigate the impact of SVG harvesting techniques – OVH vs. EVH on MACE, a composite end point of all-cause mortality, nonfatal myocardial infarction and repeat revascularization, over the active follow-up period of the study postoperatively.

Hypothesis 1: A significantly smaller proportion of CABG subjects with SVGs harvested by open technique will experience MACE post-surgery compared to CABG subjects with SVGs harvested by endoscopic technique during the active follow-up period.

Secondary Objectives:

Objective 2: To investigate the impact of SVG harvesting techniques – OVH vs. EVH on MACE, a composite endpoint of all-cause mortality, nonfatal myocardial infarction and repeat revascularization, at one and three-year postoperatively.

Hypothesis 2: One-year composite MACE rate will be 6 percentage points lower in the open harvesting group and three-year composite MACE rates will be at least 8-10 percentage points lower in the open vein harvesting group compared to the endoscopic vein harvesting group.

Objective 3: To investigate the impact of SVG harvesting techniques – OVH vs. EVH on MACE, a composite endpoint of all-cause mortality, nonfatal myocardial infarction and repeat revascularization, over the entire follow-up period (active and passive) of the study postoperatively.

Hypothesis 3: A significant smaller proportion of CABG subjects with SVGs harvested by open technique will experience MACE post-surgery compared to CABG subjects with SVGs harvested by endoscopic technique during the entire follow-up period.

Tertiary Objectives:

Objective 4: Investigate the impact of the two harvesting techniques - open vs. endoscopic - on clinical indicators of leg wound complications and subject satisfaction at six weeks post-surgery.

Hypothesis 4: Leg wound complications will be lower and satisfaction will be higher in the EVH group compared to OVH group.

Objective 5: Compare subject quality of life scores according to the SVG harvest technique at six weeks post-surgery.

Hypothesis 5: Subjects' quality of life scores will be higher in the EVH group compared to the OVH group.

Objective 6: Determine the role of vein harvester experience on clinical outcomes.

Exploratory Aim with no hypothesis specified.

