3.6 Sample Size

In the ROOBY study (CSP # 517) (Shroyer et al. 2009), 1-year MACE rates were 9.9% in the OVH group and 15.3% in the EVH group ($p=0.0025$). The executive committee for the REGROUP study assumed that during the REGROUP study, 15.5% of the participants in the EVH group will experience MACE in the first year post surgery. The committee also expects a 6 percentage point improvement in the 1-year MACE rate in the OVH group.

To detect the expected 6 percentage point difference in 1-year MACE rates between EVH (15.5%) and OVH (9.5%), a sample size of 545 in each group will be required at 85% power, 5% type-I error rate and with a two-sided test. Since, it would be possible to capture the majority of the MACE from the VA databases even if participants drop out before the one-year clinic visit, a relatively small inflation factor of 5% is used to inflate the sample size to account for the drop-outs. Thus, a total of 1,150 participants need to be randomized in the study to achieve the said power.

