7.2 Secondary Outcomes

Secondary objectives of this study include investigating the impact of SVG harvesting techniques – OVH vs. EVH on MACE at one and three-years postoperatively and over the entire follow-up period (active and passive, ~ 6.5 years) of the study postoperatively. The proportion of participants experiencing a MACE (yes/no) in the first year of follow-up after index CABG surgery date will be calculated, both collectively and by SVG harvesting technique, OVH vs. EVH. These two proportions will be compared using Pearson's chi-square test. The proportion of participants experiencing a MACE (yes-1/no-0) in the three years of follow-up after index CABG surgery date will be similarly analyzed (TABLE 26).

Assessing MACE over the entire follow-up period (active and passive) of the study postoperatively will be analyzed similarly (TABLE 21, FIGURE 2, TABLE 25) to the primary outcome with now the outcome being time (from index CABG surgery date) until the event of interest, MACE, or time-to-MACE during the entire follow-up (~ 6.5 years). Events from both the active and passive follow-up periods will be considered, whereas the primary analysis only included events from the active follow-up period. Only the first event among participants will be considered as the MACE event.

The hypotheses for the secondary aims of this study are:

H2: One-year composite MACE rate will be 6 percentage points lower in the open harvesting group and three-year composite MACE rates will be at least 8-10 percentage points lower in the open vein harvesting group compared to the endoscopic vein harvesting group.

H3: A significant smaller proportion of CABG subjects with SVGs harvested by open technique will experience MACE post-surgery compared to CABG subjects with SVGs harvested by endoscopic technique during the entire follow-up period.

The hypothesis H2 will be supported when the percent of participants experiencing MACE at one-year is 6% and at least 8% greater at three-years among those randomized to EVH vs. OVH, with a significant corresponding *p*-value < α observed for each test. The hypothesis H3 will be supported when an increased risk of MACE is observed among participants randomized to EVH, confirmed with a hazards ratio (HR) > 1.00 for EVH vs. OVH and a significant corresponding *p*-value. A total (recurrent) event analysis at various time points will also be explored comparing EVH and OVH.

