Center	Rate of Reporting	Participant ID	Protocol Non-Compliance Code	Date of Deviation
Albuquerque (501)				
...				
... and so on				

FIGURE 2: Kaplan-Meier Survival Curves

[figure not shown]

TABLE 25: MACE, Active Follow-up: Results of Multivariable Cox Proportional Hazards Regression Model

Parameter	DF	Parameter Estimate	Standard Error	Chi-Square Test Statistic	p-value	Hazard Ratio	95% Hazard CI
EVH (vs. OVH)							
Covariate 1							
...							
... and so on							

TABLE 26: Major Adverse Cardiac Events at 1-year and 3-year, by Treatment

		OVH		EVH		Total		p-value
		N	%	N	%	N	%	
1-Year	MACE							
	Death							----
	MI							----
	RR							----
3-Year	MACE							
	Death							----
	MI							----
	RR							----

TABLE 27: Leg Incision Healing by Treatment

	OVH		EVH		Total		p-value
	N	%	N	%	N	%	
No Disturbance							----
Complication (Any Disturbance)							

TABLE 28: Leg Incision Healing by Treatment: Results of Multivariable Logistic Regression Model

Parameter	DF	Parameter Estimate	Standard Error	Chi-Square Test Statistic	p-value	Odds Ratio	95% CI
EVH (vs. OVH)							
Covariate 1							
...							
... and so on							

TABLE 29: Seattle Angina Questionnaire: Change from Baseline by Treatment

			OVH		EVH		Total		p-value
			N	%	N	%	N	%	
[Component scale]	6-week	Improved							
		No Change							----
		Worsened							-----
	12-month	Improved							
		No Change							----
		Worsened							-----

* No change = (mean score change < 5)

TABLE 30: Seattle Angina Questionnaire: Results of ANCOVA Model

		Parameter	DF	Parameter Estimate	Standard Error	t-Test Statistic	p-value
[Component scale]	[6-week /12-month]	Intercept					
		Baseline Score					
		EVH (vs. OVH)					
		Interaction (if needed)					

TABLE 31: Impact and Severity of Incisional Leg Pain at by Treatment

		OVH		EVH		Total		p-value
		N	%	N	%	N	%	
Discharge	Little or no impact (impact score ≤ 50)							
	Some impact ($50 < \text{impact score} \leq 57$)							----
	Substantial impact ($57 < \text{impact score} \leq 63$)							----
	Severe impact (impact score > 63)							----
	Severe (per severity rating) (Score of 3 or above)							
6-Weeks	Little or no impact (impact score ≤ 50)							
	Some impact ($50 < \text{impact score} \leq 57$)							----
	Substantial impact ($57 < \text{impact score} \leq 63$)							----
	Severe impact (impact score > 63)							----
	Severe (per severity rating) (Score of 3 or above)							

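### The SAP's rule for supporting H2 cuts the observed one-year difference at the assumed 6 points and, read literally, rejects a larger one

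*SAP*

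**What the plan says.** H2 is worded as a size of effect. Protocol III.D states "One-year composite MACE rate will be 6 percentage points lower in the open harvesting group", and SAP 2.1 repeats this and continues "three-year composite MACE rates will be at least 8-10 percentage points lower in the open vein harvesting group". SAP 7.2 turns it into a decision rule on the excess in the EVH arm: "The hypothesis H2 will be supported when the percent of participants experiencing MACE at one-year is 6% and at least 8% greater at three-years". Significance is a further condition, to be "observed for each test". The section gives no other route to supporting H2 and no verdict for a significant one-year difference that is not 6%.

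The 6 points is the planning effect. Protocol XVII.A says "The committee also expects a 6 percentage point improvement in the one-year MACE rate in the OVH group", and SAP 3.6 sizes the trial on 15.5% vs 9.5%: "a sample size of 545 in each group will be required at 85% power, 5% type-I error rate and with a two-sided test".

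The protocol's analysis of the same endpoints (XVII.D.3) sets no minimum difference: "These two proportions will be compared using a chi-square test". The SAP's rules for H1 and H3 need a hazard ratio above 1.00 and significance; those for H4 and H5 need direction and significance. The shell for "TABLE 26: Major Adverse Cardiac Events at 1-year and 3-year, by Treatment" has columns for N, % and p-value, but none for the difference or its confidence interval.

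**The concern.** There are two problems, both at one year.

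1. **The wording cannot be programmed without a guess.** The three-year condition is a minimum; the one-year condition, in the same sentence, is a bare 6%. It could mean exactly 6, a value that rounds to 6, or at least 6. On the literal reading a larger advantage for OVH counts against H2.
2. **The cutoff sits at the assumed effect.** An estimate falls below its true value about half the time, so requiring the observed difference to reach 6 fails about half of trials in which 6 is exactly right.

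At stake is the stated verdict on one secondary hypothesis, whose one- and three-year results are a planned publication (Protocol XVIII.B). A trial could show a significant one-year advantage for OVH and still have to report H2 as not supported, and Table 26 would not show how compatible the data are with 6 or 8-10 points.

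**Working it through.** **Inputs.** SAP 3.6: 15.5% (EVH) vs 9.5% (OVH), two-sided 5%, 85% power, 545 per group, 1,150 randomized (575 per arm at equal allocation). SAP 7.2: Pearson chi-square and the H2 rule.

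**Plan's own figure.** With pooled rate p̄ = (0.155 + 0.095)/2 = 0.125,

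n = [1.960·√(2·0.125·0.875) + 1.036·√(0.155·0.845 + 0.095·0.905)]² / 0.06² = (0.9167 + 0.4827)² / 0.0036 = 544.01, rounded up to **545**. Inflation: 1,090/0.95 = 1,147.4, so 1,148, stated as about 1,150. The 85% is the power of the test against zero difference.

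**Smallest significant difference.** 1.960·√(2·0.125·0.875/n) = 3.9 points at 545 and 3.8 at 575. Differences from about 4 to just under 6 points are therefore significant but below the cutoff.

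**One-year condition.** Exact enumeration of two independent binomials, chi-square without continuity correction, significant in favour of OVH:

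| Truth 15.5% vs 9.5% | 545/arm | 575/arm |
|---|---|---|
| Significant for OVH | 85.4% | 87.3% |
| and difference at least 6.0 | 50.7% | 49.9% |
| and difference at least 5.5 | 61.5% | 60.5% |
| and difference 5.5 to under 6.5 (rounds to 6) | 21.7% | 21.2% |
| and difference 6.5 or more | 39.8% | 39.4% |

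Significant but not supporting H2:
- Cut at 6.0: 85.4 − 50.7 = 34.7% and, before rounding, 37.3% at 575.
- Cut at 5.5: 23.8% (before rounding) and 87.3 − 60.5 = 26.8%, or 26.7% before rounding.
- Overall range: 24% to 37%.

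**Literal reading.** Only about 21-22% of trials round to a whole 6%. With the SAP's one-decimal rounding and equal arms, no whole-number difference in events gives 6.0%: 32/545 = 5.9% and 33/545 = 6.1%; 34/575 = 5.9% and 35/575 = 6.1%. A larger true effect makes this worse: at 17.5% vs 9.5%, 97.4%/98.0% of trials are significant but only 13.1%/12.7% round to 6.

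**At the prior-trial rates** (15.3% vs 9.9%, Protocol XVII.A): significant 77%/79%; at least 6 points 39%/38%.

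**Joint rule (assumed three-year rates).** The documents give no three-year rates by arm. Taking OVH at 12-22%, a true three-year gap of 8-10 points, three-year events nested on one-year events, and 400,000 simulated trials per scenario, the rule read as at least 6 and at least 8 is met in 36-50% of trials at 545 per arm (37-50% at 575). Both tests are significant in 78-85% (80-87%).

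**When H2 as worded is false.** Assume 575 per arm, OVH 9.5% and 17%, and true gaps of 5 points at one year and 6 at three. Both tests are significant in about 64% of trials; the rule read as at least 6 and at least 8 is met in about 15%. With gaps of 4 and 4 the figures are 36% and 3%.

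**The case against.** The best defence is that the rule follows the hypothesis. H1 and H3 claim a significantly smaller proportion and get a significance rule; H2 claims particular sizes and gets a size rule. A significant 4-point difference does not show that OVH is 6 points better, so recording H2 as not supported is accurate on its own terms. This stands, and it rules out the simplest repair. Calling H2 supported on significance alone, with its 6 and 8-10 points left in place, would declare support in about 64% of trials when the true gaps are 5 and 6 points.

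It is also fair that the 50% figure is nearly a general truth about estimates, and that an intent to reject larger benefits is hard to credit. The first does not make the observed value a good test of a size claim; an interval does that better. The second shows only that the sentence needs its missing words.

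Three stronger readings are tempting and not supported:
- That the rule undercuts the stated 85% power. That power is for the chi-square test, which is still run and reported; none is claimed for H2.
- That the three-year 8 is a sample-size input. Protocol XVII.B does use an 8-point difference (83.5% vs 91.5% free of MACE, 532 per group, 97.5% power), but for the end of active follow-up. The 8 in SAP 7.2 is the lower end of H2's own range.
- That false-positive risk rises or the primary conclusion is touched. The rule only adds conditions, and H1 is decided separately.

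**Conclusion.** The point holds in a limited form. The one-year condition is ambiguous and, taken literally, fails about 40% of trials for having a significant difference of 6.5 points or more at the planning rates. Read as at least 6, it is met about half the time when 6 is exactly true (61% with a 5.5 cut), leaving 24-37% of trials significant for OVH at one year but not supporting H2.

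The one-year figures use only the plan's rates and sample sizes, with equal arms and complete one-year status. The joint and intermediate-gap figures rest on assumed three-year rates and show direction only. Table 26 would still give counts, percentages and p-values, so a reader could recover the differences. Severity: minor, one secondary hypothesis.

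**What to change.** In SAP 7.2:

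1. Replace the bare one-year 6% with *at least 6 percentage points greater*.
2. Give two separate verdicts. **Superiority:** the two-sided Pearson chi-square favours OVH at p<0.05 at both one and three years. **Magnitude:** whether each observed difference, with its 95% CI, is compatible with the hypothesised 6 and 8-10 points.
3. Add a difference (95% CI) column to Table 26.
4. If the point-estimate cutoff is kept for the magnitude verdict, state that its one-year part is met only about 50% of the time when the true difference is 6.

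Do not report H2 as supported on significance alone unless its statement in Protocol III.D, SAP 2.1 and SAP 7.2 is reworded as a superiority claim, with 6 and 8-10 points as expected effects.

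Cost: a rewritten SAP passage and one table column, with no new data. The protocol changes only if H2 itself is reworded.

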7.3 Tertiary Outcomes

Tertiary objectives of this study include investigating the impact of SVG harvesting techniques – OVH vs. EVH on leg wound complication, patient satisfaction, and quality of life in addition to determining the role of vein harvester's experience on clinical outcomes.

All participants will be examined for post-operative complications of the leg wound from harvesting at discharge and at six weeks post-surgery. Post-operative leg wound complication status (yes-1/no-0) will be determined. The proportion of participants with leg wound complications will be computed for each treatment group and these proportions will be compared using Pearson's chi-square test (TABLE 27). The impact of confounding variables, such as BMI, diabetes status, and smoking status, on post-operative leg wound infection will be analyzed using multivariable logistic regression (TABLE 28). Surgical site infections at the vein harvest site according to the Center for Disease Control criteria will be explored.

Patient satisfaction will be assessed using the "Treatment Satisfaction" scale of the Seattle Angina Questionnaire. Participants will be categorized as "improved", "no change" and "worsened" at 6 weeks and 12 months compared to their baseline scores (TABLE 29). The proportion of participants in these three categories will be compared between the two groups using Pearson's chi-square test. The actual scores from these measures will also be used to compare harvesting techniques using analysis of covariance (ANCOVA) techniques, where the baseline (pre-surgery) scores will be used as a covariate (TABLE 30).

The occurrence of severe leg pain, due to incisions made during vein grafting, will be collected at discharge and 4-6 weeks post-CABG. The proportion of participants with severe pain (yes = pain severity rating score ≥ 3) at each time point will be compared across groups using Pearson's chi-square test (TABLE 31).

Quality of life scores using the PCS and MCS of the VR-12 and the "Quality of Life" scale of the Seattle Angina Questionnaire will be computed at baseline, six weeks, and 12 months post-surgery for participants in each SVG harvesting group. For each component of the VR-12 (PCS and MCS), mean changes from baseline at six weeks and 12 months will be computed and compared using ANCOVA (TABLE 32).

For each scale of the SAQ (angina stability, angina frequency, physical limitation, treatment satisfaction, & quality of life), participants will be categorized as “improved”, “no change” and “worsened” at 6-weeks and 12 months compared to their baseline scores (TABLE 29). The proportion of participants in these three categories at each time point will be compared between the two groups using Pearson's chi-square test. The actual scores from these measures and that of the VR-12 MCS and PCS will be used to compare harvesting techniques using ANCOVA techniques, where the baseline (pre-surgery) scores will be used as a covariate (TABLE 30).

The hypotheses for the tertiary aims of this study are:

H4: Leg wound complications will be lower and satisfaction will be higher in the EVH group compared to OVH group.

H5: Subjects' quality of life scores will be higher in the EVH group compared to the OVH group.

H6: Exploratory Aim with no hypothesis specified.

The leg wound complication component of hypothesis H4 will be supported when the percent of participants experiencing leg wound complications randomized to EVH is lower than that of participants randomized to OVH with a significant *p*-value observed. Higher patient satisfaction in the EVH group vs. OVH group will be supported by a significant effect for treatment when entered into the ANCOVA model and a positive coefficient for EVH vs. OVH. The hypothesis H5 will be supported by a significant effect for treatment when entered into the ANCOVA model and a positive coefficient for EVH vs. OVH for the outcomes of SAQ quality of life scale, VR-12 PCS, and VR-12 MCS.

